7.3 Disease Assessment

See [Section 9.0](#) for disease assessment time points (approximately every 12 weeks). Disease assessment timing (cystoscopy, urine cytology, and biopsy) is to be based on calendar timing counted as weeks after registration, not based on cycles or drug administration.

Week 13:

Office cystoscopy and urine cytology will be performed 13 weeks after registration. Patients with suspicious cystoscopy or cytology findings positive for malignancy at 13 weeks (or at any other disease assessment time point) must undergo further evaluation with TURBT/biopsy, and patients with high-grade T1 or higher stage recurrences will be taken off protocol treatment. Persistent Ta or CIS at 13 weeks and low-grade recurrences at any timepoint will be tolerated without treatment interruption.

Only frankly malignant cytology (equivalent to Papanicolaou class V) will be considered "positive" and used to determine the need for bladder biopsy and further evaluation. Cytology is limited by its subjectivity and poor reproducibility so that lower grades of possible cytologic abnormalities cannot be used reliably. All patients will undergo close monitoring of the urine cytology, so that adverse changes will be noted promptly.

Week 25:

Complete response for patients with CIS component will be assessed with urine cytology, cystoscopy, and **mandatory** bladder biopsy at Week 25 (within \pm 7 days of the start of Week 25, regardless of treatment delays). If patient is found to have persistent CIS or other high-grade disease, patient will be removed from protocol treatment. Patients with CIS at study entry achieving a complete response at 25 weeks will continue on protocol therapy as planned.

CIS patients with suspicious cystoscopy findings or cytology positive for malignancy at Week 13 and a negative biopsy at Week 13 are not required to undergo the mandatory Week 25 biopsy if their Week 25 cystoscopy is not suspicious and Week 25 cytology is negative for malignancy. A patient with positive cytology but negative biopsy at Week 25

must have re-evaluation of the upper tracts via CT or MRI (including CT-IVP, CT-urogram or MR-urogram) of the abdomen and pelvis (males and females) and biopsy of the prostatic urethra (males only).

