- α Atezolizumab is given every 21 days. Vital signs should be monitored before, during, and after infusion. See [Section 7.2](#) for details.
- Σ To be performed within two weeks prior to registration
- ¥ To be performed more frequently if clinically indicated.
- ≠ Disease assessment will be performed every 3 months (12 weeks) for the first 2 years, then every 6 months (24 weeks) for Years 3-5 until HG recurrence or death. Disease assessment includes office cystoscopy and cytology A biopsy is required for suspicious cystoscopy findings or cytology results positive for malignancy.
- # Following a HIGH-GRADE recurrence within 5 years after registration, disease assessment is at discretion of treating investigator and the **S1605** Disease Assessment Form does not need to be submitted. However, the **S1605** Follow-up Form is still required for the full 5 year duration or death.
- f Bladder biopsy is REQUIRED for patients with any component of CIS at study entry (with or without concomitant Ta/T1 disease) within 7 days of Week 25 after registration, except where noted in [Section 7.3](#). All patients with suspicious cystoscopy findings or cytology positive for malignancy at any of the indicated diseases assessment times (or any other time, i.e. for cause) will undergo biopsy or TURBT. Patient should continue receiving atezolizumab while waiting for biopsy. Submit Pathology report for all biopsies performed, regardless of result.
- π Submit FFPE tissue any time a biopsy is performed for suspected recurrence of any type or persistent CIS.
- ι The CT or MRI scan must be performed at Week 73 for all patients who have not had a HG recurrence before that timepoint and scans must be submitted via AG Mednet. See [Section 15.2](#) for instructions.
- § Submit all cytology reports as a RAVE source document.
- Ω Follow-up safety assessments are required at 30 days and 90 days after the last dose of atezolizumab, regardless if patient has started a new cancer therapy. Report ALL toxicities, ALL Grades for first 30 days following last dose of protocol treatment on the last S1605 Adverse Event Form. Report ALL toxicities, ≥ Grade 3 for days 31-90 following last dose of protocol treatment on the **S1605** Late Effects Form. Amend original Late Effects form to add any additional toxicities ≥ Grade 3 experienced throughout remaining follow-up period.

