10.0 CRITERIA FOR EVALUATION AND ENDPOINT ANALYSIS

10.1 Complete Response

Complete Response: Negative biopsy for high grade disease at Week 25 (\pm 7 days) for the subset of patients with a CIS component at study entry, according to local pathology call. In addition, patients with a CIS component who undergo negative biopsy at Week 13 for suspicious cystoscopy and or positive cytology and have cystoscopy not suspicious for cancer and cytology not positive for malignant cells at Week 25 do not require repeat biopsy at Week 25 and will be considered to have a complete response at Week 13 and will also be counted as having a complete response at Week 25.

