10.2 Complete Response duration

Complete Response Duration: Defined as the time from date of biopsy documenting the complete response to the time of first high-grade recurrence.

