11.0 STATISTICAL CONSIDERATIONS

11.1 Patient Populations

Eligible patients are defined as registered patients who met all the pre-registration eligibility criteria listed in Section 5 that were in effect at the time of the 12/14/18 amendment. The determination of eligibility regarding Disease Related Criteria will be based on local pathology review.

Evaluable patients are defined as registered patients who received any amount of study drug (atezolizumab).

Efficacy analyses will be based on patients who are determined to be both eligible and evaluable as defined above.

Safety analyses will be based on patients who are determined to be evaluable as defined above. Patients who are registered in the study but who do not receive any study drug will not be included in safety analyses.

11.2 Estimate of Sample Size:

A sample size of 135 eligible patients (evaluable) will be enrolled over 36 months with 18 months of additional follow-up. Our goal is to enroll 70 patients with a CIS component and 65 patients with Ta or T1 disease only. One stratum may be closed prior to accrual completion to ensure adequate patient numbers in both disease groups. An additional 50% will be enrolled to account for ineligibility or initial treatment refusal resulting in a total sample size of 202. With Revision #5 (Version Date 12/14/18) a pre-registration Study Chair approval form was enacted which has significantly reduced the rate of ineligible registrations.

11.3 Analysis:

There will be two co-primary aims for this study: The first objective to be tested involves the complete response rate in the subset of patients with CIS (see [Section 10.1](#)). The second co-primary objective involves event-free survival at 18 months for all evaluable patients. A hierarchical approach will be used to test the two co-primary aims. The CIS aim will be tested first. Only if the result is statistically significant will the second primary objective be evaluated. Only patients who received at least one dose of atezolizumab per protocol will be evaluable for these two primary objectives. Both co-primary tests will be conducted at the one-sided 0.05 significance level.

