The first primary objective is the estimation of the CR rate in the subset of patients with CIS. Enrollment of 70 eligible and evaluable patients with a CIS component will be ensured. If the total number of patients out of 70 who respond is 28 (40%) or greater, the agent would be considered promising. This design has a significance level (probability of falsely declaring that an agent with a 30% complete response probability is worthy of further investigation) of 4.6%, and a power (probability of correctly declaring than an agent with a complete response rate of 50% is worthy of further investigation) of 96%. Seventy evaluable patients are sufficient to estimate the CR rate at 25 weeks (± 1 week) to within $\pm 12\%$ (95% confidence interval). Those CIS patients without a biopsy at 25 weeks will be assumed to be non-responders. Duration of CR is defined as the time from date of biopsy documenting the complete response to the time of first high-grade recurrence, and is a key additional secondary endpoint. With a CR rate of 50%, we would expect 35 patients would have a CR. We can estimate the proportion still in CR at 18 months to within $\pm 17\%$ (95% confidence interval).

One interim futility assessment will be made in the CIS subset. We will evaluate the first 25 eligible and evaluable CIS patients for pathologic response at 25 weeks. Since accrual is expected to be slow, accrual will continue while the interim evaluation is underway. A favorable evaluation would be if 7 or more CRs are seen in the first 25 eligible and evaluable CIS patients. This is equivalent to testing the alternative hypothesis of a 50% complete response rate at the one-sided $\alpha=0.02$. If results are favorable, accrual will continue to a total of 70 eligible and evaluable CIS patients.

The second primary endpoint is event-free survival (EFS) (as defined in [Section 10.0](#)) at 18 months in the mixed population of patients with either CIS or Ta or T1 disease. This objective will only be tested if the null hypothesis in the first co-primary objective is rejected as specified above. The 18-month EFS estimate will be obtained using the method of Kaplan and Meier, and the Greenwood formula will be used to estimate the variance. A 90% confidence interval will be estimated for the 18-month EFS estimate. If the lower 90% confidence bound excludes 20%, the investigators will conclude the regimen significantly improves EFS relative to historical trial data.

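### Section 11.3 scores every CIS patient without a Week 25 biopsy as a non-responder, including those whom Section 10.1 excuses from that biopsy and counts as complete responders

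*Combined protocol and SAP*

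**What the plan says.** Section 10.1 defines complete response for patients with a CIS component as a biopsy negative for high-grade disease at Week 25, by local pathology. It then adds a second route, for patients who had a negative biopsy at Week 13, taken because of suspicious cystoscopy or positive cytology, and who have clear cystoscopy and cytology at Week 25. The second biopsy is waived for them and their response is dated to Week 13. As to the Week 25 endpoint, the section states that they "will also be counted as having a complete response at Week 25".

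Two other sections carry the same exemption. Section 7.3 says that these patients "are not required to undergo the mandatory Week 25 biopsy if their Week 25 cystoscopy is not suspicious" and the cytology is negative. The bladder-biopsy footnote to the Section 9.1 calendar requires the biopsy "within 7 days of Week 25 after registration, except where noted in" Section 7.3.

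Section 11.3 refers to Section 10.1 when it introduces the complete-response objective. Its scoring sentence, however, reads: "Those CIS patients without a biopsy at 25 weeks will be assumed to be non-responders". The interim futility look is introduced with "We will evaluate the first 25 eligible and evaluable CIS patients for pathologic response at 25 weeks", and its decision rule then counts complete responses, with 7 or more of 25 needed to continue.

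Duration of response in Section 10.2 is "Defined as the time from date of biopsy documenting the complete response to the time of first high-grade recurrence".

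**The concern.** The exemption reached Sections 7.3, 9.1 and 10.1 but not the statistical section. Applied as written, the Section 11.3 sentence turns patients who followed the protocol, and whom the endpoint definition calls responders, into failures.

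Three things depend on this score:

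- **First co-primary endpoint.** Success needs 28 of 70. Event-free survival is tested only if this succeeds.
- **Interim futility look.** Continuing needs 7 of the first 25. The introductory wording speaks of pathologic response at 25 weeks, but an exempt patient's only pathology in support of response is from Week 13.
- **Duration of response.** On the literal reading, exempt patients drop out of the responder set. If Section 10.1 governs there is no difficulty, because their start date is that of the negative Week 13 biopsy.

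Both decisions rest on fixed counts, so one patient scored differently can change the result near a cut-off. In a single-arm trial, choosing between two written rules once the data are known would be hard to defend.

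**Working it through.** **The two rules applied to one patient.** Take a CIS patient with suspicious cystoscopy at Week 13, a negative biopsy at Week 13, clear cystoscopy and cytology at Week 25, and no Week 25 biopsy.

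| Section | Result for this patient |
|---|---|
| 7.3 and 9.1 | Week 25 biopsy not required |
| 10.1 | Complete response at Week 25 |
| 11.3, scoring sentence | Non-responder |

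**Inputs (Section 11.3).** n = 70; success at 28 or more; continue past the interim at 7 or more of the first 25; null rate 30%; alternative rate 50%; stated significance level 4.6% and power 96%.

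**Reproducing the plan's figures.** Let b(x; 25, p) be the binomial probability of x responders among the first 25, and R the total needed. The probability of success is

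P(p, R) = sum over x = 7 to 25 of b(x; 25, p) × Pr[Bin(45, p) ≥ R − x].

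- P(0.30, 28) = 0.0464, stated as 4.6%.
- P(0.50, 28) = 0.9597, stated as 96%.

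Both agree. Without the interim look the values are 0.0476 and 0.9639, so the stated figures include it. They depend only on n, the cut-offs and the rates, and are not in dispute.

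**Effect of the literal rule, by count.** The documents do not give the number of exempt responders, so k is an assumption. If k exempt responders are scored as failures at the final analysis only, the number of Section 10.1 responders needed becomes R = 28 + k.

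| k | R | Power at true 50% | Type I error at true 30% |
|---|---|---|---|
| 0 | 28 | 0.960 | 0.046 |
| 1 | 29 | 0.937 | 0.027 |
| 2 | 30 | 0.903 | 0.015 |
| 3 | 31 | 0.857 | 0.008 |

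**Effect by share.** If a fraction f of true responders is exempt, the scored rate is p(1 − f), with R = 28 and the interim also affected. At a 50% rate the expected number of responders is 0.50 × 70 = 35, so f = 2% is 0.7 patients and f = 5% is 1.75 patients.

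| f | Power at true 50% | Type I error at true 30% | Interim passed at true 50% |
|---|---|---|---|
| 0 | 0.960 | 0.046 | 0.993 |
| 2% | 0.943 | 0.036 | 0.990 |
| 5% | 0.910 | 0.025 | 0.986 |
| 10% | 0.824 | 0.012 | 0.974 |
| 20% | 0.537 | 0.002 | 0.926 |

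Power is 0.900 at f = 2/35 = 5.7% and first falls below 0.90 at about 5.8%. The 10% and 20% rows are outer bounds with no support in the documents.

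**The case against.** The documents go a long way towards resolving the conflict themselves. Section 10.1 sits in the part of the protocol that sets the criteria for endpoint analysis, it names exactly these patients, and it states their score. Section 11.3 refers to it. If the specific rule governs the general one, the Section 11.3 sentence covers only required biopsies that are missing; the literal reading would leave an explicit sentence of Section 10.1 without effect. The interim rule counts complete responses, the term that Section 10.1 defines. The duration problem arises only on the less likely reading. The exempt group is narrow, its size is unknown, and a repeat biopsy is not forbidden. With one or two such patients, power stays at or above 0.90. The literal reading cannot produce a false claim of efficacy. On this view, the point is a minor clarification.

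Most of this stands. The likely intent can be recovered, the realistic effect is probably small, and the error is conservative. What does not stand is that the text settles the matter. No passage gives an order of precedence, and the Section 11.3 sentence refers neither to missing nor to required biopsies: it describes patients without a Week 25 biopsy, which is exactly what exempt patients are. The scoring of a gatekeeping endpoint should not rest on inferred intent.

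**Conclusion.** The concern holds. The Section 11.3 sentence is wrong as written because it lacks an exception, and it contradicts the endpoint definition to which that section itself refers. The error does not touch the stated operating characteristics, which reproduce.

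Its size depends on how many responders use the exemption, which is not known. With one or two misscored at the final analysis, power falls by about 2 to 6 percentage points (0.960 to 0.937 or 0.903); with three, by about 10 (to 0.857). Type I error falls in every case. The harm is limited to a missed effect on complete response and, through the hierarchy, an event-free survival test that is not carried out. It arises only if Section 11.3 is applied literally, there is at least one exempt responder, and the count lies close to 28, or close to 7 at the interim. The sentence should be corrected because of the endpoint's role and because correcting it is easy; a large effect has not been shown.

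**What to change.** Add an exception to the Section 11.3 sentence, for example: *CIS patients who have no Week 25 biopsy are scored as non-responders, except those who meet the Section 10.1 provision for no repeat biopsy, who are scored as complete responders; the interim assessment uses the same rule.*

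This brings the scoring into line with the existing endpoint definition and leaves the assessment schedule as it is. It also settles who enters the duration-of-response analysis. A sensitivity count with the exempt patients scored as non-responders is optional.

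The cost is one clause in one sentence. No new data are needed, and the sample size and both cut-offs stay the same.

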Based on published rates (see table below), it is assumed that if the true 18-month EFS rate in this mixed patient population is $\leq 20\%$, then this regimen will not warrant further investigation in this setting, whereas a 30% or greater EFS rate at 18 months would be of

considerable interest. This study has a type I error rate (one-sided) of 0.05 and statistical power of 0.93.

There will be one interim analysis conducted at the end of accrual. The 99% confidence interval around the 18 month EFS Kaplan-Meier estimate will be constructed. If the upper confidence bound rules out 30% then consideration will be given to reporting the results early due to futility. There is no adjustment to the alpha for this interim test because it is based on futility. We will not consider reporting early due to efficacy. Because one of the primary endpoints occurs at 18 months and accrual is expected to be steady but modest, an interim analysis of EFS prior to this point in the trial will not be informative.

There are several trials with outcomes that can be used as historical controls for this trial. Most of these are described in [Section 2.0](#).

Drug	Study	Patients	Outcome
Valrubicin	Steinberg 2000	BCG-unresponsive CIS	21% @ 3 mo 17% @ 12 mo 8% @ 24 mo
Valrubicin	Dinney 2013	BCG-unresponsive CIS	10% @ 12 mo 3% @ 24 mo
Gemcitabine	Skinner 2013	mostly BCG unresponsive CIS/Ta/T1 (89% high grade)	28% @ 12 mo 20% @ 24 mo
Gemcitabine	DiLorenzo 2010	mix of BCG failure/unresponsive	19% @ 24 mo
Docetaxel	Lamont 2005	mix of BCG failure/unresponsive	40% @ 12 mo 25% @ 36 mo
MCNA	Morales 2015	mix of BCG failure/unresponsive	20.9% @ 12 mo (FDA analysis)
rAdIFN	Dinney 2015	BCG unresponsive CIS/Ta/T1	35% @ 1 mo

Only Valrubicin is FDA approved in this setting, and is therefore the most representative historic control. Compared to all of these studies, our intended endpoint of 30% EFS at 18 months would demonstrate a clear improvement in outcome.

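### The EFS power of 0.93 in Section 11.3 is a marginal figure that leaves out the CR gate; at the plan's own alternatives the gate costs at most about 4 points, and more if CR is below 50%

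*Combined protocol and SAP*

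**What the plan says.** Section 11.3 (Analysis) sets a fixed sequence for the two co-primary aims, CR in the CIS subset first and 18-month EFS in all patients second. The rule appears twice: "Only if the result is statistically significant will the second primary objective be evaluated" and, under the second endpoint, "This objective will only be tested if the null hypothesis in the first co-primary objective is rejected as specified above". On alpha it says "Both co-primary tests will be conducted at the one-sided 0.05 significance level".

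The CR rule is "If the total number of patients out of 70 who respond is 28 (40%) or greater, the agent would be considered promising". Its stated error rate is 4.6% at a true CR rate of 30%, and its stated power is 96% at 50%. A futility look comes first: "A favorable evaluation would be if 7 or more CRs are seen in the first 25 eligible and evaluable CIS patients".

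For EFS, success means that the lower 90% confidence bound of the Kaplan-Meier estimate (Greenwood variance) excludes 20%, and 30% is the rate of interest. The power statement reads "This study has a type I error rate (one-sided) of 0.05 and statistical power of 0.93". It mentions neither a CR rate nor the gate, and Section 11 gives no power for the whole sequence.

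**The concern.** A positive EFS conclusion requires at least 7 CRs in the first 25 CIS patients, at least 28 in 70, and then an EFS lower bound above 20%. A power attributed to the study would normally be the probability of that whole path. The CR figures are of this kind, since 4.6% and 96% match the calculation that includes the 7/25 look. The EFS figure is not.

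The 65 Ta/T1 patients count towards EFS but not towards the gate. If the CR rate in CIS falls short of 50% while EFS in the mixed population is still 30%, the EFS question may never be formally tested, and the quoted 0.93 does not show how often.

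**Working it through.** **Inputs from Sections 11.2 and 11.3.** 135 patients (70 CIS, 65 Ta/T1); 36 months of accrual plus 18 months of follow-up; EFS 20% vs 30% at 18 months; one-sided 0.05; CR 30% vs 50%; CR rules 7/25 and 28/70.

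**Step 1: reproduce 0.93.** Assume exponential EFS and uniform accrual.
- Hazards: λ0 = −ln(0.20)/18 = 0.0894 and λ1 = −ln(0.30)/18 = 0.0669, so ln(λ0/λ1) = 0.290.
- Expected events under 30%: d = n × {1 − [exp(−18λ1) − exp(−54λ1)]/(36λ1)} = 119.7 for n = 135.
- Power = Φ(0.290 × √119.7 − 1.645) = 0.937, against the stated 0.93.
- The same formula for the Ta/T1 subset (n = 65, d = 57.6) gives 0.712, against the stated 71%.

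This is very probably the method used. No CR quantity enters it.

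**Step 2: the gate.** P(gate) = Σ over x = 7 to 25 of Bin(x; 25, p) × P(Bin(45, p) ≥ 28 − x).

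| True CR | 28/70 alone | with 7/25 look |
|---|---|---|
| 30% | 0.0476 | 0.0464 |
| 40% | 0.545 | 0.537 |
| 45% | 0.832 | 0.824 |
| 50% | 0.964 | 0.960 |

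The right-hand column gives the stated 4.6% at CR 30% and the stated 96% at CR 50%.

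**Step 3: gated power starting from 0.93.**
- Whatever the dependence at CR 50%, the joint probability is at least 0.960 + 0.93 − 1 = 0.89 and at most 0.93.
- Under independence it is 0.960 × 0.93 = 0.89.
- Section 10.4 counts high-grade Ta or CIS at Week 25 or later as an EFS event, so CIS patients free of events at 18 months are nearly all responders and the two tests are positively correlated. With 30% EFS in both strata, ρ = 70 × 0.30(1 − p)/√[70p(1 − p) × 135 × 0.21], which is 0.47 at p = 0.50. A bivariate normal calculation then gives 0.90, or 0.91 starting from 0.937.
- From 0.93, independence to nested: 0.77–0.79 at CR 45% and 0.50–0.53 at CR 40%.

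**Step 4: gated power under the stated EFS rule.** Without censoring, Greenwood reduces to the binomial variance.
- 35/135: 0.2593 − 1.645 × √(0.2593 × 0.7407/135) = 0.197, which does not exclude 20%.
- 36/135: 0.2667 − 1.645 × √(0.2667 × 0.7333/135) = 0.204, which does.

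The rule is therefore at least 36/135. Its exact type I error is 0.037 and its marginal power at 30% is 0.826.

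For the joint event, CIS EFS successes are drawn only from responders. CIS 18-month EFS e runs from 0.20 to 0.30, and Ta/T1 EFS is (0.30 × 135 − 70e)/65, that is 0.41 down to 0.30, so the mixture stays at 30%. There is no dropout.

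| True CR | P(gate) | P(gate and ≥36/135) |
|---|---|---|
| 50% | 0.96 | 0.81 |
| 45% | 0.82 | 0.71–0.72 |
| 40% | 0.54 | 0.49–0.50 |

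The marginal value is about 0.83 throughout.

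**The case against.** In a fixed-sequence design it is ordinary practice to quote each endpoint's marginal power at its own alternative, and 0.93 follows directly after the EFS hypotheses. The gate is disclosed twice, beside the CR power of 96%, so a reader can bound the joint power at 0.93 + 0.96 − 1 = 0.89. Withholding the EFS test when CR fails is the purpose of the hierarchy. CR rates of 45% and 40% lie below the design alternative, where any test loses power. EFS in the Ta/T1 subset is a separate secondary aim with its own stated power of 71%, and no gate is placed on it.

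Most of this stands. It rules out three inferences that a reader might draw:
- That 0.93 is an arithmetic error. It is a legitimate marginal figure for the calculation apparently used.
- That the gate undermines the design or its alpha. The gate cannot raise the type I error of the EFS test, and the cost at the design alternatives is small.
- That the reader has no way to see the effect. At the design alternatives the bound is available by hand.

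What does not stand is the attribution. The sentence credits the study with 0.93, and the design with its gate does not have that power for an EFS conclusion. The CR figures in the same section do cover their full decision path.

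**Conclusion.** The point holds as one of labelling and completeness. The stated 0.93 is marginal power. With the gate, the probability of a positive EFS conclusion at CR 50% and EFS 30% is about 0.89–0.91 starting from 0.93 (bounds 0.89–0.93), and about 0.81 rather than 0.83 under the stated Greenwood rule. The loss is 2 to 4 points. Large losses appear only when the true CR rate is below 50%: at 40% the gate opens about 54% of the time, even if EFS is 30%.

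The gate pass probabilities and the 0.89–0.93 bounds need no assumption about dependence. The other gated figures rest on assumptions that the documents do not supply:
- CIS non-responders are EFS failures. This is approximate, because 11.3 counts a missing Week 25 biopsy as non-response while 10.4 does not make it an EFS event.
- CIS 18-month EFS is 20–30%; varying it over this range moves the Greenwood-rule results by 2 points or less.
- There is no dropout.

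Why 0.93 differs from the 0.83 given by the Greenwood rule is a separate question. It matters here only for which rule the gated figures should use.

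**What to change.** In Section 11.3:
1. Label the EFS power as marginal, ignoring the CR gate. Do not call it the power once the EFS test is reached. That is conditional power, which is higher because CR and EFS are positively related: under the 36/135 rule about 0.81/0.96 = 0.84 at CR 50% and 0.90–0.94 at CR 40%, against 0.83 marginal.
2. Add the gated power at CR 50% and EFS 30%, with CR 45% and 40% as sensitivity values. Compute it with the stated rule (at least 36/135 without censoring): marginal about 0.83; gated about 0.81, 0.71–0.72 and 0.49–0.50. State the three assumptions.
3. Do not lower the cut-off to recover 0.93. At least 33/135 would give marginal power of about 0.936, but its exact type I error is 0.12 and its lower limit of 0.184 does not exclude 20%.

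The cost is a wording change and a slightly less favourable stated power. Conduct, sample size and alpha are unchanged.

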1.2 Secondary Objective(s)

- a. To estimate event-free survival at 18 months for the subset of patients with papillary cancer (Ta/T1).
- b. To estimate progression-free survival, cystectomy-free survival, bladder cancer-specific survival, overall survival in all patients.

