10.7 Event-Free Survival

Event-Free Survival: From date of registration to first documentation of event (see [Section 10.4](#)). Patients last known to be alive and not to have recurred are censored at the date of last contact.

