A secondary aim of interest is the assessment of EFS in the Ta/T1 subset. With n=65 eligible and evaluable patients, there will be 71% power to detect Ho: 20% vs. Ha: 30%, using a one-sided alpha=0.05. Other secondary estimates and confidence intervals of endpoints of progression-free survival (PFS), cystectomy-free survival, bladder cancer specific survival (CSS) and overall survival (OS) will also be provided using Kaplan-Meier estimation. Short-term estimates at 18 months and long-term estimates at 5 years for these secondary endpoints will be of interest. Qualitative and quantitative toxicity assessment will be provided using CTCAE reporting. CR and adverse event rates can be estimated to within $\pm 9\%$ (95% confidence interval). A toxicity with a true incidence of 1% (5%) has a 69% (99%) chance of being observed at least once in this single arm trial.

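### The stated power of 0.93 for 18-month EFS is not the power of the plan's own Kaplan-Meier/Greenwood rule, which is about 0.83 at one-sided 0.05

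*Combined protocol and SAP*

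**What the plan says.** Section 11.2 sets the size and calendar: "A sample size of 135 eligible patients (evaluable) will be enrolled over 36 months with 18 months of additional follow-up". Section 11.3 fixes the level: "Both co-primary tests will be conducted at the one-sided 0.05 significance level".

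Section 11.3 then defines the EFS test. The 18-month estimate is "obtained using the method of Kaplan and Meier, and the Greenwood formula will be used to estimate the variance", a 90% confidence interval is formed, and "If the lower 90% confidence bound excludes 20%, the investigators will conclude the regimen significantly improves EFS relative to historical trial data". The scale on which the interval is built (plain, log, log-log or other) is not given. The rates of interest are 20% or less (not worth pursuing) and 30% or more (of considerable interest), followed by: "This study has a type I error rate (one-sided) of 0.05 and statistical power of 0.93".

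For the papillary subset, Section 11.3 says: "With n=65 eligible and evaluable patients, there will be 71% power to detect Ho: 20% vs. Ha: 30%, using a one-sided alpha=0.05". It gives no decision rule there, and Section 1.2 words that aim as estimation. Section 10.7 governs censoring: "Patients last known to be alive and not to have recurred are censored at the date of last contact". No loss rate after the start of treatment is stated; the 50% inflation in Section 11.2 covers only ineligibility and initial treatment refusal.

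**The concern.** A power statement placed directly after a decision rule will be read as the power of that rule. A 10-point difference tested on 135 patients with a binomial-type variance cannot be expected to reach 0.93 at one-sided 0.05.

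The figure does not change the test or its outcome. It changes how a negative result is read: with power 0.93, failing to exclude 20% looks like fairly strong evidence against a true rate of 30%; with 0.83 it is weaker evidence. The same applies to Ta/T1 if a test is intended there. The unnamed scale is a related gap, because one possible result, 35 of 135 event-free, succeeds on some scales and fails on others.

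**Working it through.** **Inputs.** n=135, 36 months of accrual, 18 months of further follow-up (11.2); one-sided alpha 0.05, 20% vs 30%, Kaplan-Meier with Greenwood variance, lower 90% limit above 20% (11.3); Ta/T1 n=65 with the same rates and alpha (11.3). The 90% interval is read as two-sided, so its lower limit tests at one-sided 0.05.

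**Step 1: where 0.93 and 71% may come from.** Take a one-sample exponential test using all events over the study.
- Hazards: λ0 = −ln(0.20)/18 = 0.0894 and λ1 = −ln(0.30)/18 = 0.0669 per month; ln(λ0/λ1) = 0.290.
- Probability of an event under the alternative, with uniform accrual: 1 − (e^(−18λ1) − e^(−54λ1))/(36λ1) = 0.887. Expected events d: 135 × 0.887 = 119.7 and 65 × 0.887 = 57.6.
- Power = Φ(0.290·√d − 1.645) = 0.937 (n=135) and 0.712 (n=65).

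Both are close to the stated figures. A log-scale normal approximation, Φ(ln(1.5)/√(0.7/(0.3n)) − 1.645), gives 0.925 and 0.690, also fairly close. The plan names neither, so the source is an inference.

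**Step 2: power of the written rule, no early loss.** The last patient enrolled has 18 months of follow-up. If nobody is lost earlier, the Kaplan-Meier estimate is the simple proportion p = r/n and Greenwood's variance is p(1−p)/n. The lower limit at each r then decides success, and alpha and power are exact binomial tails at 0.20 and 0.30.

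| n | r | plain limit | log-log limit | log limit | exact alpha | exact power |
|---|---|---|---|---|---|---|
| 135 | 33 | 0.184 | 0.186 | 0.191 | 0.120 | 0.936 |
| 135 | 34 | 0.1904 | 0.1929 | 0.1973 | 0.084 | 0.907 |
| 135 | 35 | 0.1972 | 0.1995 | 0.2041 | 0.057 | 0.871 |
| 135 | 36 | 0.2041 | 0.2063 | 0.2109 | 0.037 | 0.826 |
| 65 | 18 | 0.186 | 0.1902 | 0.1992 | 0.085 | 0.701 |
| 65 | 19 | 0.1995 | 0.2035 | 0.213 | 0.049 | 0.600 |
| 65 | 20 | 0.2135 | 0.217 | 0.227 | 0.026 | 0.493 |

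- n=135: plain and log-log need 36, power 0.826. Log and logit (logit limit 0.2022 at 35) need 35, power 0.871, but alpha exceeds 0.05.
- To reach 0.93 the cut-off would have to be 33/135, at alpha 0.120.
- n=65: log-log, log and logit need 19, power 0.600; plain needs 20, power 0.493. Even 18/65 gives only 0.701.

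**Step 3: early loss.** The documents give no rate, so 5%, 10% and 20% lost by 18 months were assumed, with exponential event and loss times and 20,000 simulated trials per setting. On the log-log scale:

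| Assumed loss by 18 months | 5% | 10% | 20% |
|---|---|---|---|
| Power, n=135 | 0.837 | 0.825 | 0.799 |
| Alpha, n=135 | 0.047 | 0.044 | 0.046 |
| Power, n=65 | 0.565 | 0.549 | 0.524 |
| Alpha, n=65 | 0.043 | 0.042 | 0.048 |

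Across plain, log and log-log scales and 0 to 20% loss, the highest power found was 0.87 at n=135 and 0.63 at n=65.

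**The case against.** **The figures are not slips.** Both stated powers match one ordinary exponential calculation, so the fault is an unnamed planning model that differs from the analysis rule. That is probably right, but it does not rescue the statement. The exponential calculation counts events after 18 months, which the written rule ignores. It also needs a constant hazard, which is doubtful when Ta and CIS count as events only from Week 25 (Section 10.4).

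**0.83 depends on a scale the plan does not state.** True: the range is 0.83 to 0.87. The upper end breaks the plan's own alpha, so 0.83 is the figure consistent with one-sided 0.05. Reading the 90% limit as one-sided does not help either. On the plain or log-log scale it gives power 0.907 at alpha 0.084.

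**The hierarchical gate is left out.** EFS is tested only if the CIS test succeeds, so 0.826 holds given that the gate is passed. With gate power 0.964 at a 50% response rate, the chance of passing both lies between 0.826 + 0.964 − 1 = 0.790 and 0.826. This stands as a clarification. The stated 0.93 ignores the gate too, and the gate can only lower the unconditional figure.

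**Ta/T1 contradicts no stated rule.** Correct, so that part is conditional. Even so, hypotheses, alpha and power are given there without a test, and the reader cannot tell what the 71% refers to.

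**The dropout figures are assumptions.** They are, and should be labelled so wherever they are used.

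**Conclusion.** The concern holds. Under the rule in Section 11.3, power for 20% vs 30% at n=135 is 0.826, not 0.93, on any scale examined that keeps one-sided alpha at or below 0.05. On the log or logit scale it is 0.871 with alpha 0.057. The miss probability at a true 30% is 1 − 0.826 = 0.174, about two and a half times the implied 0.07. These values assume that every patient is followed to 18 months or to an event, and that the CIS test has been passed. Assumed loss of 10 to 20% gives about 0.80 to 0.83 on the log-log scale. For Ta/T1, if the same rule applies, power without loss is 0.600 or 0.493 against the stated 71%.

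The design remains reasonable at about 80% power or more for the co-primary test, given the gate and over that loss range on the log-log scale. What is wrong is the reported operating characteristic, with a small but real ambiguity in the decision at 35/135.

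**What to change.** In Section 11.3:

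1. After the sentence on Greenwood's variance, name the interval scale. Complementary log-log is one suitable choice: without early censoring its exact alpha is 0.037 at n=135 and 0.049 at n=65.
2. Replace 0.93 with about 0.83 (36/135 needed), stating that this assumes complete follow-up to 18 months or an event and, preferably, that it is conditional on a significant CIS test. Add about 0.80 to 0.83 under 10 to 20% early loss, labelled as an assumption.
3. Say whether the same rule is applied to Ta/T1. If so, replace 71% with about 0.60 (19/65 needed) without loss, and about 0.52 to 0.55 under the same assumed loss. If the aim is estimation only, remove the power statement.
4. If 0.93 and 71% come from another planning model, name it and its assumptions, and show its figures only beside the power of the actual rule.

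This is wording only. Sample size, the 20% threshold and alpha are unchanged. The cost is a less favourable stated power. Keeping 0.93 under the written rule would instead need about 205 evaluable patients by the normal approximation with the alternative variance: (1.645 + 1.476)² × 0.21/0.10² ≈ 205.
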